2.2.2. Justification for Dose

The safety and efficacy outcomes from the Phase 2 study, INCB 18424-211, can be summarized as follows:

- All ruxolitinib cream treatment arms demonstrated efficacy and superiority over vehicle in F-VASI50 and F-VASI75 at Week 24 with a clear separation from vehicle emerging by Week 12.
- At Week 24, 1.5% QD and BID treatment regimens further separate from the 0.15% and 0.5% treatment regimens with the highest response at Week 24 in F-VASI50 (50.0%) in the 1.5% QD regimen.
- The 1.5% BID treatment regimen demonstrated the highest response for F-VASI75 at both Week 24 (30.3%) and Week 52 (51.5%). T-VASI50 response in the 1.5% BID regimen was modest at Week 24 (12.1%); however, this regimen also demonstrated the highest response for T-VASI50 (36.4%) at Week 52, and it is recognized that repigmentation on nonfacial areas proceeds slower than on facial areas.
- All ruxolitinib treatment arms were generally safe and well-tolerated with no significant TEAEs or application site events and no clinically relevant hematological changes through Week 52.

Based on the above data, the proposed treatment regimen of ruxolitinib cream for the Phase 3 studies is 1.5% BID. Limiting treatment to up to 10% BSA will limit exposure and potentially improve the benefit-risk.

2.3. Benefit/Risk Assessment

In nonclinical studies, ruxolitinib cream did not act as a contact sensitizer, nor did it produce significant dermal irritation or demonstrate phototoxicity or photoallergenic potential. The lack of adverse cutaneous effects has been supported by clinical studies to date, where cutaneous AEs have been infrequent and of similar frequency and severity as with vehicle control treatment. Long-term immune suppression may occur with JAK inhibition, which could potentially increase the risk of cutaneous viral skin infections and nonmelanoma skin cancers. Participants should be monitored accordingly.

The primary clinical risks noted with orally administered ruxolitinib treatment for polycythemia vera or myelofibrosis are the potential sequelae of decreased hematopoietic proliferation secondary to the inhibition of growth factor pathways by JAK2 antagonism. Dose-dependent, reversible thrombocytopenia has been observed in participants with myelofibrosis, as well as anemia and less frequently neutropenia. An increased rate of infection is an additional potential risk of immunomodulation. In healthy participants and rheumatoid arthritis participants with greater bone marrow reserve, the effects on hematopoietic proliferation appear to be less pronounced. Owing to its low systemic bioavailability, ruxolitinib cream is not expected to bring about clinically significant changes in hematology laboratory investigations.

Based on Week 24 and Week 52 results of the Phase 2 study, INCB 18424-211, all active treatment groups were found to have no clinically relevant AEs related to the treatment regimens and were well-tolerated on application sites. They were also unremarkable for laboratory values, vital signs, or physical examinations. While minor changes in select hematology parameters (red blood cells and platelet counts) were noted in the laboratory assessments, they were mostly within the limits of the normal range of values, transient, asymptomatic, and clinically insignificant and did not necessitate any remedial action.

Currently, there are no approved therapies for vitiligo, and treatments are empirical and directed by the available clinical guidelines. Current therapies often do not lead to satisfactory response, and there are limitations and safety concerns with long-term use of some therapies, including topical or oral corticosteroids and calcineurin inhibitors. Given the psychosocial burden and stigma that has been reported in this disease, patients with vitiligo warrant access to new studies.

In summary, ruxolitinib cream 1.5% BID can be safely used as a topical medication for vitiligo and represents the treatment regimen with the best benefit-to-risk ratio from among those investigated. More detailed information about the known and expected benefits and risks and reasonably expected AEs of ruxolitinib cream may be found in the ruxolitinib cream IB.

3. OBJECTIVES AND ENDPOINTS

Table 4 presents the objectives and endpoints.

Table 4: Objectives and Endpoints

Objectives	Endpoints				
Primary					
To evaluate the duration of clinical response of ruxolitinib cream in participants with vitiligo.	For participants who are randomized in Cohort A: • Time to relapse (defined as < F-VASI75).				
Key Secondary					
To evaluate the duration of clinical response of ruxolitinib cream in participants with vitiligo.	For participants who are randomized in Cohort A: • Time to maintain ≥ F-VASI90 response.				
Secondary					
To further evaluate the efficacy of ruxolitinib cream.	 Proportion of participants who achieve F-VASI50/75/90 during the extension treatment period. Actual measurements, change, and percentage change from baseline in F-VASI. Proportion of participants who achieve T-VASI50/75/90 during the extension treatment period. 				
	 Actual measurements, change, and percentage change from baseline in T-VASI. Actual measurements, change, and percentage 				
	 change from baseline in F-BSA. Actual measurements, change, and percentage change from baseline in T-BSA. Proportion of participants achieving a VNS of "4 – A lot less noticeable" or "5 – No longer noticeable" during the extension treatment period. 				
To determine the participants' quality of life	Change from Week 52 in DLQI (or CDLQI) during the extension treatment period.				
To evaluate the safety and tolerability of ruxolitinib cream.	The frequency and severity of AEs; includes performing physical examinations and collecting vital signs and laboratory data for hematology and serum chemistry.				
To evaluate the ruxolitinib PK in plasma after treatment with ruxolitinib cream.	• Trough plasma concentrations of ruxolitinib at Week 80 and Week 104.				

Table 4: Objectives and Endpoints (Continued)

Objectives	Endpoints

4. STUDY DESIGN

4.1. Overall Design

This is a Phase 3, double-blind, vehicle-controlled, randomized withdrawal and treatment extension study that will enroll eligible participants who have completed either Study INCB 18424-306 or Study INCB 18424-307 (parent studies) in which the participants will have been using ruxolitinib cream 1.5% BID for the previous 28 to 52 weeks (depending on their initial randomization in the parent study; see Figure 1).

The parent studies are randomized, vehicle-controlled studies in adolescent and adult participants (age \geq 12 years) with non-segmental vitiligo who have depigmented area including \geq 0.5% BSA on the face, \geq 0.5 F-VASI, \geq 3% BSA on nonfacial areas, and \geq 3 T-VASI. Total body involved vitiligo area (facial and nonfacial) was not to exceed 10% BSA. Approximately 300 participants per each parent study were to be randomized 2:1 to receive an initial, double-blind study treatment of ruxolitinib cream 1.5% BID or vehicle (applied to depigmented vitiligo areas on the face and body up to 10% total BSA) for 24 weeks. After completion of the Week 24 assessments, participants in these studies were offered the opportunity to receive an additional 28 weeks of open-label treatment extension with ruxolitinib cream 1.5% BID under the parent study protocol.

Participants who successfully complete the 52-week treatment in either of the parent studies (ie, 52 weeks ruxolitinib cream or 24 weeks vehicle plus 28 weeks ruxolitinib cream) and tolerated ruxolitinib treatment without safety concern and with good compliance for continuation may be eligible to participate in this treatment extension study.

Visits in this treatment extension study are named to reflect continuation from the parent studies, with the first visit of this treatment extension study occurring at Week 52. The eligibility assessment for this extension study occurs at Week 52. The treatment extension period of this study comprises the period from the Week 52 visit to the Week 104 visit (inclusive). Following the last application of study treatment at Week 104, there will be a 30-day safety follow-up period to evaluate safety and duration of response. Figure 1 presents the study design schema, and Table 3 presents the SoA.

The purpose of this extension study is to evaluate the duration of response under randomized withdrawal of ruxolitinib cream and maintenance of response with continued use of ruxolitinib cream, in vitiligo patients who have experienced repigmentation with ruxolitinib cream treatment, as well as to provide long-term efficacy and safety data in vitiligo patients, regardless of how quickly or completely they responded to treatment initially. Eligible participants in this study will be assigned to 1 of 2 cohorts, Cohort A or Cohort B, based on their F-VASI responses at the time of enrollment in this study (ie, at Week 52).

Treatment in Cohort A is a randomized withdrawal design and will provide data on the duration of response following withdrawal of ruxolitinib cream and maintenance of response with its continued use. Participants who achieve complete or almost complete facial repigmentation (ie, achieve ≥ F-VASI90) at Week 52 in the parent study will be assigned to Cohort A and will be stratified by the original treatment received on study Day 1 of the parent study and randomized 1:1 to treatment with vehicle cream BID or ruxolitinib cream 1.5% BID for an additional 52 weeks (ie, until EOT at Week 104). However, any participants in Cohort A who

experience relapse (defined as < F-VASI75) will receive ruxolitinib cream 1.5% BID as an open-label rescue treatment until they complete treatment (Week 104 or EOT).

Treatment in Cohort B will provide long-term efficacy and safety data for ruxolitinib cream in vitiligo patients. Participants who did not achieve ≥ F-VASI90 at Week 52 of the parent studies will be assigned to Cohort B and will continue ruxolitinib cream 1.5% BID for 52 weeks (ie, until EOT Week 104).

For Cohort A, the participant, investigator, and sponsor will remain blinded to treatment assignment; the treatment for Cohort B will be open-label.

During this extension study, participants will receive study treatment (ruxolitinib cream 1.5% BID or vehicle) for 52 weeks to be applied to depigmented areas on the face and body; the total treated areas (facial plus nonfacial areas) should not exceed 10% BSA. Participants should continue to treat depigmented areas identified for treatment at baseline of the parent study even if the area begins to improve or fully repigment.

Thus, depending on their initial randomized treatment in the parent study and the treatment to which they are randomized at Week 52 in this extension study, participants will have received ruxolitinib cream 1.5% BID for a minimum of 28 weeks and a maximum of 104 weeks.

Safety endpoints, such as nature of AEs (type, frequency, and severity includes performing targeted physical examination and collecting vital signs and routine laboratory investigations) will be monitored and recorded throughout the course of this study.

4.2. Overall Study Duration

Eligibility will be evaluated on the first day of this extension study, which occurs on the same day as the parent study Week 52 visit; the treatment extension period is 52 weeks; and safety follow-up is 30 days. Total duration of this study is approximately 56 weeks (see Figure 1).

The study will begin when the first participant (or parent or guardian) signs the ICF. The end of the study is defined as the date of the last visit of the last participant in the study or the date that the last participant discontinued study drug and completed applicable safety follow-up assessments or is lost to follow-up. A participant is considered to have completed the study if he/she has completed all study visits, including the safety follow-up visit.

4.3. Study Termination

The investigator retains the right to terminate study participation at any time, according to the terms specified in the study contract. The investigator is to notify the IRB/IEC in writing of the study's completion or early termination, send a copy of the notification to the sponsor or sponsor's designee, and retain 1 copy for the site study regulatory file.

The sponsor may terminate the study electively or if required by regulatory agency. In the event of significant safety findings, the study will be terminated. If the study is terminated prematurely, the sponsor or designee will notify the investigators, the IRBs/IECs, and regulatory bodies of the decision and reason for termination of the study.

5. STUDY POPULATION

Deviations from eligibility criteria are not allowed because they can potentially jeopardize the scientific integrity of the study, regulatory acceptability, and/or participant safety. Therefore, adherence to the criteria as specified in the Protocol is essential. Prospective approval of Protocol deviations to recruitment and enrollment criteria, also known as Protocol waivers or exemptions, are not permitted.

5.1. Inclusion Criteria

Participants are eligible to be included in the study only if all of the following criteria apply:

- 1. Currently enrolled and receiving treatment in INCB 18424-306 or INCB 18424-307 studies evaluating ruxolitinib cream in participants with vitiligo.
 - Note: Eligibility criteria for INCB 18424-306 or INCB 18424-307 are provided in Appendix A.
- 2. Currently tolerating ruxolitinib cream in the parent study and no safety concerns per investigators judgment.
- 3. Has demonstrated compliance, as assessed by the investigator, with the parent study protocol requirements.
- 4. Willingness and ability to comply with scheduled visits, treatment plans, and any other study procedures indicated in this protocol.
- 5. Male and female participants must be willing to take appropriate contraceptive measures to avoid pregnancy or fathering a child for the duration of study participation with the exception of the following:
 - a. Females of non-childbearing potential (ie, or surgically sterile with a hysterectomy and/or bilateral oophorectomy OR postmenopausal, ≥ 12 months of amenorrhea without an alternative medical cause).
 - b. Prepubescent adolescents (age 12-18 years old at the time enrolled in parent studies). Note: Information about specific types of acceptable contraceptive measures and duration of contraceptive use are provided in Appendix B.
- 6. For adult participant, ability to comprehend and willingness to sign an ICF; for adolescent participant, written informed consent of the parent(s) or legal guardian and written assent from the adolescent participant when possible.
 - Note: Adolescents, who during the course of the study become legal adults, will be asked for their consent to continue the study, and in the event of lack thereof, will be discontinued from further participation.

5.2. Exclusion Criteria

Participants are excluded from the study if any of the following criteria apply:

- 1. Has been permanently discontinued from study treatment in the parent study for any reason.
- 2. Participants with an uncontrolled intercurrent illness or any concurrent condition that, in the investigator's opinion, would jeopardize the safety of the participant or compliance with the Protocol.

Note: See information provided in Exclusion Criterion 4 of the INCB 18424-306/ INCB 18424-307 parent study protocol (Appendix A); the investigator should consult with the sponsor medical monitor if there are any questions regarding uncontrolled intercurrent illness or any concurrent condition that may be exclusionary.

- 3. Pregnant or breastfeeding woman.
- 4. Participants who live with anyone participating in any current Incyte-sponsored ruxolitinib cream study.

5.3. Lifestyle Considerations

Participants should continue to avoid excessive exposure to artificial sunlight (including tanning booths, sun lamps, etc).

If sunscreen, makeup, or other cosmetics have been applied to the areas to be treated, participants should follow the application guidance (see Section 6.6.1).

It is recommended that swimming should not take place within 2 hours before and after the planned study drug application.

Study drug should be applied at least 2 hours after shaving.

5.4. Screen Failures

Screen failures are defined as participants who consent to participate in the clinical study but are not subsequently entered in the study.

5.5. Replacement of Participants

Participants will not be replaced during the study.

6. STUDY TREATMENT

See Appendix D for COVID-19–related guidance.

6.1. Study Treatments Administered

Table 5 presents the study treatment information.

Table 5: Study Treatment Information

Study treatment name:	Ruxolitinib	Vehicle			
Dosage formulation:	Cream				
Unit dose strength(s)/dosage level(s):	1.5%	Not applicable			
Route of administration:	Topical				
Administration instructions:	BID. A thin film is applied to depigmented vitiligo areas.	BID. A thin film is applied to the depigmented vitiligo areas.			
Packaging and labeling:	Ruxolitinib cream and vehicle cream will be provided in 60 g tube. Each tube will be labeled as required per country requirement.				
Storage:	Ambient (15°C-30°C/59°F-86°F)				
Status of treatment in participating countries:	Investigational	Not applicable			

On visit days, study drug will be applied in the clinic during the visit. Participants should remove study drug from the tube in fingertip units until all of the areas to be treated are covered by a thin film; the tube will be weighed before and after application to determine the participant's dosage. On the day of a visit, the participant should not apply the study drug at home and will apply study drug from the new kit in the clinic. Participants will be instructed to document treated areas and be advised to limit use to no more than one 60 g tube per week. Application instructions will be provided by the site study staff, and the participants will record their daily applications via a diary card given to the participants during each study visit. Refer to the Study Pharmacy Manual for participant instructions for handling of study drug.

At any time, if vitiligo areas become significantly more extensive than from the previous visit, the participant should contact the study site to discuss with the investigator whether additional evaluation at the clinic is required. If any other skin products that are permitted under the study Protocol are used, participants should continue these unchanged during the study.

During the treatment extension period, participants should follow the below study drug application guidance:

- All participants in Cohort A will use their randomly assigned treatment (either vehicle or ruxolitinib cream) on both the face and total body.
- Participants should apply study drug to depigmented vitiligo areas up to a T-BSA (facial and nonfacial) of $\leq 10\%$ BSA.

- Participants should continue to treat all depigmented vitiligo areas identified for treatment at baseline (Day 1 of the parent study) even if the area begins to improve or fully repigment.
- Participants who have an expansion of existing areas of vitiligo or develop new vitiligo lesions during the course of the treatment extension period may treat these areas after a visit to document the VASI score and other measures of vitiligo (may be unscheduled visit), as long as the new treated T-BSA (facial and nonfacial) does not exceed 10% BSA. Newly developing vitiligo lesions should be documented in the eCRF. The VASI scores for these new lesions should not be calculated with or combined together with treated areas identified at baseline (Day1 of parent study).

6.2. Preparation, Handling, and Accountability

The investigator or designee must confirm and document that appropriate temperature conditions (both ruxolitinib cream and vehicle cream are to be stored between 15°C and 30°C [59°F-86°F]) have been maintained during transit for all study treatments received and that any discrepancies are reported and resolved before use of the study treatment.

Only participants enrolled in the study may receive study treatment, and only authorized site staff may supply study treatment. Immediately after application of ruxolitinib cream, participants are to wash their hands thoroughly with soap and warm water (unless the area to be treated includes the hands). Refer to the Study Pharmacy Manual for participant instructions for handling of study drug.

All study treatment must be stored in a secure, environmentally controlled, and monitored (manual or automated) area in accordance with the labeled storage conditions, with access limited to the investigator and authorized site staff. Participants should store study treatment at ambient temperature conditions.

The investigator (or designee) is responsible for study treatment accountability, reconciliation, and record maintenance (ie, receipt, reconciliation, and final disposition records). Inventory and accountability records must be maintained and readily available for inspection by the study monitor and are open to inspection at any time by any applicable regulatory authorities. The investigator or designee must maintain records that document:

- Delivery of study drug(s) to the study site.
- Inventory of study drug(s) at the site.
- Participant use of the study drug(s) including tube counts from each supply dispensed.
- Return of study drug(s) to the investigator or designee by participants.

The investigational product must be used only in accordance with the Protocol. The investigator will also maintain records adequately documenting that the participants were provided the specified study drug. These records should include dates, quantities, and any available batch or serial numbers or unique code numbers assigned to the investigational product and study participants.

Completed accountability records will be archived by the site. The investigator or designee will be expected to collect and retain all used, unused, and partially used containers of study drug until verified by the study monitor (unless otherwise agreed to by the sponsor). At the conclusion of the study, the investigator or designee will oversee shipment of any remaining study drug back to the sponsor or its designee for destruction according to institutional SOPs. If local procedures mandate on-site destruction of investigational supply, the site should (where local procedures allow) maintain the investigational supply until the study monitor inspects the accountability records in order to evaluate compliance and accuracy of accountability by the investigative site. At sites where the study drug is destroyed before monitor inspection, the monitors rely on documentation of destruction per the site SOP.

Further guidance and information for the final disposition of unused study treatments are provided in the study materials provided to sites.

6.3. Measures to Minimize Bias: Randomization and Blinding

All participants will be centrally assigned to study treatment using an IRT system. For Cohort A, the system will assign in a 1:1 ratio (ruxolitinib cream 1.5% BID:vehicle). For Cohort B, the system will assign all participants to ruxolitinib cream 1.5% BID.

The IRT will track participant visits, randomize participants according to the defined parameters, maintain the blinding (Cohort A only), and manage study drug inventory. Full details will be provided in the IRT Manual. Study treatment will be dispensed at the study visits summarized in the SoA (see Table 3).

For Cohort A, the participant, investigator, and sponsor will remain blinded to treatment assignment; the treatment for Cohort B will be open-label. After the database lock for the primary analysis (Week 104), the participant, the investigator, and the sponsor will be unblinded.

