8.4. Pharmacokinetic Assessments

Venous blood samples will be collected to assess the PK of ruxolitinib cream in participants at each study visit indicated in Table 3.

The exact date and time of the PK blood draws and the date and time of the last application of study drug preceding the blood draw (if applicable) will be recorded in the eCRF.

Instructions for sample preparation and shipping will be provided in the Laboratory Manual. Participants will receive reminder cards in advance of the study visit providing instruction to hold the application of study drug on the day of the visit and a place to record the time of the prior dose of study drug.

Pharmacokinetic blood samples can be collected at any time prior to study drug application at the site at the Week 80 visit and at any time at the W104 (EOT) visit. Blood samples must not be drawn from the area that has been treated with study drug. If it is not possible to access an area that is not treated with study drug, the site must adequately document this in the eCRF and not take the PK blood sample for that visit. After the PK sample is drawn, participants will apply ruxolitinib cream 1.5% or vehicle cream at the site.

All analyses will be conducted by Incyte Corporation (Wilmington, DE) or Incyte's designee.

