7.1. General Considerations

For all continuous variables, both the actual value, change, and percentage from baseline (if available) will be analyzed.

All by-visit analyses will include the follow-up period if the data are available.

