9. PLANNED ANALYSES

The primary analysis will occur after the primary database lock, when all participants have completed the vehicle-controlled, double-blind treatment period.

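### Participants and investigators are unblinded at the Week 104 lock, which is not tied to the last 30 (+7) day follow-up visit, so some Cohort A follow-up could be scored with the arm known

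*Protocol*

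**What the plan says.** **Who is blinded, and until when.** Protocol 6.3 sets the rule: "For Cohort A, the participant, investigator, and sponsor will remain blinded to treatment assignment". It then ends the blind for all three parties at one point: "After the database lock for the primary analysis (Week 104), the participant, the investigator, and the sponsor will be unblinded".

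**When the lock happens.** SAP 9 says: "The primary analysis will occur after the primary database lock, when all participants have completed the vehicle-controlled, double-blind treatment period". Protocol 4.1 defines the treatment extension period as running from Week 52 through Week 104, so the follow-up visit lies outside it.

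**What follow-up is for.** Protocol 4.1 says that after the last application "there will be a 30-day safety follow-up period to evaluate safety and duration of response". Protocol 8.8 places the visit 30 (+7) days after end of treatment. The follow-up column of Table 3 marks adverse events, F-BSA, T-BSA, F-VASI, T-VASI, the facial photo-and-mirror assessment (the VNS, as Protocol 8.2.6.1 describes it) and DLQI/CDLQI.

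**Whether the data are used.** SAP 7.1: "All by-visit analyses will include the follow-up period if the data are available". SAP 8.2.1 counts adverse events as treatment-emergent up to 30 days after the last dose.

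Neither document makes the lock, or the unblinding of sites and participants, wait for the last follow-up visit. Neither requires follow-up to be scored blind.

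**The concern.** The rule removes the blind from the people who produce the data while some of those data may still be outstanding. F-VASI and T-VASI are visual estimates by the investigator (Protocol 8.2.2), VNS is the participant's own judgement (8.2.6.1), and adverse event causality is an investigator judgement (9.3). Each can shift once the rater knows whether the participant was withdrawn to vehicle or kept on ruxolitinib. A rater who expects pigment loss after withdrawal may see more of it, and one who knows the participant had vehicle may be less ready to call an event related.

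At stake is whether the off-treatment comparison of the two Cohort A arms, and the last month of the adverse event window, are blinded for everyone or only for those who finished early.

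**Working it through.** **Step 1. Order of events for the last Cohort A participant.**

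| Event | Timing | Source |
|---|---|---|
| End of double-blind treatment | Week 104 | Protocol 4.1 |
| Earliest primary lock | once all have completed that period | SAP 9 |
| Participants and investigators unblinded | after that lock | Protocol 6.3 |
| Follow-up visit | 30 to 37 days after end of treatment | Protocol 8.8 |

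Nothing fixes the order of the last two rows. It depends on the lag from the last Week 104 visit to the lock.

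**Step 2. Share exposed.** The plan gives no figure to reproduce. Let L be the days from the last Cohort A Week 104 visit to the lock and unblinding, and E the days over which Week 104 visits are spread, assumed even. A participant is exposed if the follow-up visit is still due at unblinding:

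share = max(0, D − L) / E, with D = 30 to 37 days.

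The documents give neither L nor E. I take E = 182, 365 and 548 days (6, 12 and 18 months) and vary L.

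| Lag L (days) | E = 182 | E = 365 | E = 548 |
|---|---|---|---|
| 0 | 16.5% to 20.3% | 8.2% to 10.1% | 5.5% to 6.8% |
| 14 | 8.8% to 12.6% | 4.4% to 6.3% | 2.9% to 4.2% |
| 28 | 1.1% to 4.9% | 0.5% to 2.5% | 0.4% to 1.6% |
| 37 or more | 0% | 0% | 0% |

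For example, at L = 28 the extremes are (30 − 28)/548 = 0.4% and (37 − 28)/182 = 4.9%. The top of the table is 37/182 = 20.3%, which needs a lock on the day of the last Week 104 visit.

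**Step 3. Which results the exposed data can reach.**

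- *Treatment-period data, Weeks 52 to 104:* none. SAP 9 has them complete before the lock.
- *Primary analysis on that lock:* none. A score recorded after a lock cannot enter the locked data.
- *By-visit follow-up summaries:* yes, if follow-up is reported later for everyone (SAP 7.1). These are descriptive: Protocol 10.3 tests only the primary and key secondary endpoints, and SAP 3.2 calls all analyses exploratory.
- *Adverse event tables:* yes, for events reported and attributed at follow-up.

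For secondary efficacy, SAP 7.5.1 summarises Cohort A only up to the first open-label rescue dose, so rescued participants' follow-up scores drop out of those summaries. The table counts all of Cohort A and so overstates the number of efficacy scores affected.

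**The case against.** The strongest reply is that this is narrow and may never occur. The last Week 104 visit still generates central laboratory and PK samples, so a lock within days is unlikely, and by 37 days the exposure is zero. SAP 7.1 takes follow-up data only if available, so a visit not yet made at the lock is not in the analysis of that lock. SAP 9 describes only the primary analysis and names no later one that late-scored data would enter.

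Most of that stands and limits the size of the point. It does not remove it. The unblinding rule is explicit, the assessments are scheduled, and the documents give follow-up a role in judging duration of response and in the adverse event window.

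Three stronger readings are tempting and are not supported.

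- *The primary endpoint is compromised.* A reader might infer this because SAP Table 2 sets no Week 104 cut-off for relapse. But follow-up scored after the lock cannot change the analysis run on it, and no second time-to-relapse analysis is described.
- *PK results unblind the sponsor early.* Protocol 8.4 says "All analyses will be conducted by Incyte Corporation", but that sentence goes on to allow a designee. It gives no assay or release date, and Protocol 6.3 already requires the sponsor to stay blinded. Week 52 to Week 80 is 196 days, or 49 to 65 half-lives at 4 and 3 days (Protocol 2.1.2), so a measurable level in an unrescued participant would point to ruxolitinib. A zero is not conclusive, because the Phase 2 range on 1.5% BID was 0 to 662 nM. After rescue, the level says nothing about the randomized arm. This is safeguard detail left unstated, not a documented unblinding.
- *Knowledge of the arms shaped the SAP.* Nothing links PK data to the removal of Site 710, for which SAP 5.3 gives a reason, or to the absence of alpha control in SAP 3.2.

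**Conclusion.** The point holds in a limited form. As written, Protocol 6.3 and SAP 9 allow participants and investigators to learn the arm before the last Cohort A follow-up visits are scored. The exposure is conditional on a lock less than 37 days after the last Cohort A Week 104 visit. Under the assumed even spread over 6 to 18 months it is about 0% to 5% of Cohort A at a lag of 28 days or more, and reaches about 20% only with a same-day lock and the shortest enrolment. It touches descriptive follow-up and safety summaries only. The true enrolment spread and lock lag would settle the size, and the documents give neither. The change is worth making because the rule is explicit and the remedy is cheap.

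**What to change.** Separate the two unblindings in Protocol 6.3. Suggested wording:

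> The sponsor is unblinded once the primary-analysis (Week 104) database is locked. Participants and investigators are unblinded only after the last Cohort A participant has had the safety follow-up visit.

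SAP 9 can carry the same sentence. The primary analysis date does not move. Site and participant unblinding moves by at most 37 days, about five weeks, and by less the later the lock. Emergency unblinding under Protocol 9.5 is untouched.

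If the lock has already taken place, the study report can give the date of site and participant unblinding and the date of the last Cohort A follow-up visit, and flag any follow-up assessments made between them.

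Optional clarification in Protocol 8.4 and SAP 7.7: Cohort A ruxolitinib concentrations are withheld from the study team and sites until the lock. This spells out what 6.3 already requires and costs one sentence.
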